## 1.0 Objectives / Specific Aims

Following a stroke, quality of life is often limited by gait instability [1], due to increases in fall-risk [2-3] and fear of falling [4-5]. Recent large-scale interventions have failed to effectively address this problem [6-8], likely as a result of not being targeted to the mechanisms underlying post-stroke gait instability. This project will conduct initial testing of a novel rehabilitation method designed to improve post-stroke gait stability, based on mechanistic principles of motor learning. Specifically, this work is based on our promising preliminary work, in which weak mediolateral forces applied to the legs during walking using a novel force-field caused beneficial stabilizing after-effects in both neurologically intact controls and individuals who had experienced a stroke.

The first Aim is to identify the simplest force-field control method sufficient to modulate foot placement. We hypothesize that adjusting foot placement based solely on pelvis displacement will be sufficient to produce a more stable gait pattern. The second Aim (the clinical trial component) is to determine whether repeated gait practice with foot placement error-reduction or error-augmentation methods promotes retained use of the typical gait stabilization strategy. We hypothesize that error-augmentation methods will produce significantly larger effects than observed in either an error-reduction group or a control group. The third Aim is to quantify the effects of baseline characteristics and intervention dosage on the responses to error-reduction and error-augmentation methods. We hypothesize that lower-functioning individuals will benefit more from error-reduction, while higher-functioning individuals will benefit more from error-augmentation.

# 2.0 Background

Approximately 800,000 Americans experience a stroke every year [9]. During recovery, the restoration of gait function is a high-ranking goal for patients [10], as independent mobility is a primary factor influencing quality of life [11]. While existing gait rehabilitation methods can sometimes improve function, only about half of individuals who have experienced a stroke return to typical levels of community ambulation [12].

A major contributing factor to post-stroke reductions in mobility is gait instability, which can cause an increased risk of falls [2-3] and fear of falling [4-5]. Unfortunately, existing interventions focused on balance and strengthening [6], multifactorial fall prevention [7], and locomotor training [8] have failed to substantially impact gait instability, as evidenced by continued high fall incidence. These failures suggest the need for therapies focused on mechanisms specific to post-stroke instability [13]. For example, stroke survivors are more

likely to fall due to intrinsic causes (i.e. not caused by slips, trips, pushes, etc.) than agematched controls [2]. As recent results suggest the importance of targeting training toward the specific causes of losses of balance [14], interventions that reduce the risk of such internal perturbations may be particularly helpful among stroke survivors.

Our preliminary work suggests a path forward. We have demonstrated that neurologically intact controls use a consistent strategy of adjusting their foot placement in response to the mechanical state of their pelvis [15]. In contrast, we found that a sub-population of stroke survivors with increased fall-risk does not use this typical gait stabilization strategy, instead tending to simply place their paretic leg far laterally [16]. The most likely explanation for this altered post-stroke behavior is "learned non-use", in which repeated avoidance of relying on the paretic limb contributes to chronic deficits [17]. Based on principles of motor learning, the typical gait stabilization strategy may thus be restored by either encouraging participants to walk with the typical gait stabilization strategy (error-reduction) [18], or by promoting error-driven adaptation through error-augmentation [19].

In preliminary work (n=15 neurologically intact controls; n=6 chronic stroke survivors), we have tested the effects of applying weak mediolateral forces to the legs during walking, pushing the legs either toward an appropriate mechanical location (error-reduction) or away from an appropriate location (error-augmentation). We found that error-reduction methods caused beneficial increases in use of the typical gait stabilization strategy while being applied. In contrast, we found that error-augmentation methods caused improvements in the use of the typical gait stabilization strategy after application, in the form of beneficial after-effects.

The purpose of this study is to reveal whether our novel force-field methods can have a beneficial effect on the gait stabilization strategy used by chronic stroke survivors. Promising results will provide the basis for larger scale clinical trials to quantify the effects on post-stroke functional mobility.

#### 3.0 Intervention to be studied

Aim 2 of this study will involve the initial testing of an entirely novel intervention, to determine whether larger-scale testing is justified. Given the novelty of this intervention, no citations are available. However, the structure of this intervention is directly based on a well-known intervention (split-belt walking) that has the similar goal of improving the characteristics of walking among chronic stroke survivors [20].

No medications are involved in this intervention.

A novel mechanical device is involved in this intervention. Specifically, we have developed a force-field that is able to apply weak mediolateral forces to the legs of users while they walk. The device consists of linear actuators (i.e. motors) that are used to reposition trolleys within steel frames that are secured in front and behind a treadmill embedded in the floor of the laboratory. Nylon-coated wires in series with extension springs run from the trolley behind the treadmill to the trolley in front of the treadmill, always running parallel to the walking direction. These wires pass through leg cuffs strapped to the lateral sides of the users' legs, with an orientation that allows completely

free motion of the legs in the anteroposterior (forward/backward) and vertical directions. The only effect of the wires is to exert a weak mediolateral force on the legs when they deviate from the mediolateral position of the corresponding actuators.

While this intervention involves a novel device, we believe that it should be classified as having "Nonsignificant Risk". Even in comparison to devices listed by the FDA as having Nonsignificant Risk (e.g. implantable vascular access devices, electrical neuromuscular stimulators, etc.), our novel device has substantially less risk. Our device is non-invasive. In fact, the actively powered components of the device (linear actuators) do not directly interface with the users at all, and are located ~10 feet away. The largest forces that our device is able to apply to users is only ~5 pounds, a force that can be easily overcome. As reference, the forces that a treadmill exerts on the legs during walking are substantially higher than this. The wires are constrained to always run laterally to the users' legs, so there is no risk of tripping over the wires. Additionally, hard mechanical stops in the actuators prevent the wires from ever encouraging users to step off the side of the treadmill belts, or from causing cross-over steps. In summary, the novel device is entirely unable to drive users into a non-anatomical position or to directly cause a loss of balance.

While our device can thus not directly cause a fall, it is theoretically possible that stroke survivors could respond inappropriately to the forces applied, causing themselves to lose their balance. To prevent a fall in this case, participants will always wear a safety harness attached to an overhead rail. Additionally, a member of the study staff will always stand immediately next to the treadmill to provide assistance if a participant becomes uncomfortable.

Experiments using these methods of applying weak mediolateral forces to the legs during walking have previously been approved by the MUSC IRB for neurologically-intact controls (Pro00056100) and chronic stroke survivors (Pro00046775). In preliminary testing involving 15 controls and 6 stroke survivors, no participants have experienced a loss of balance or any other adverse events.

The intervention will include 54 chronic stroke survivors, divided into three groups: 1) an Error-Reduction group; 2) an Error-Augmentation group; 3) an Activity-Matched Control group. The intervention will include 24 training sessions over a 12-week period. Assessment sessions will be performed prior to beginning the intervention, every 4-weeks during the intervention, and at a 12-week follow-up. Details of the procedures are described below under Study Design / Methods.

# 4.0 Inclusion and Exclusion Criteria/ Study Population

Participants will be recruited from an MUSC database containing the contact information of stroke survivors who have agreed to be contacted for research participation (Pro00037803), and from a local VA database of stroke survivors (Pro00043107). Additionally, IRB-approved study flyers will be posted in area rehabilitation clinics and distributed through stroke support groups attended by study staff. Initial screening will be performed by study staff through a phone call to confirm basic participant characteristics (e.g. timing of stroke, ability to walk) and interest in research participation. The ability of

potential participants to meet the more detailed inclusion and exclusion criteria will subsequently be determined in person.

Inclusion Criteria will be: 1) Age >= 21 years; 2) Experience of a stroke at least 6 months prior to participation; 3) Preferred overground gait speed of at least 0.2 m/s; 4) Ability to walk at self-selected speed for 3-minutes without a cane or walker; 5) Provision of informed consent.

Exclusion Criteria will be: 1) Resting heart rate above 110 beats/min; 2) Resting blood pressure higher than 200/110 mm Hg; 3) History of congestive heart failure, unstable cardiac arrhythmias, hypertrophic cardiomyopathy, severe aortic stenosis, angina or dyspnea at rest or during activities of daily living; 4) Preexisting neurological disorders or dementia; 5) History of major head trauma; 6) Legal blindness or severe visual impairment; 7) History of DVT or pulmonary embolism within 6 months; 8) Uncontrolled diabetes with recent weight loss, diabetic coma, or frequent insulin reactions; 9) Orthopedic injuries or conditions (e.g. hip replacements) with the potential to alter the ability to adjust foot placement while walking.

It should be noted that participants will be permitted to wear daily-use orthoses or braces during walking trials, such as those used to prevent equinus issues at the ankle.

This research will include women and minorities to the extent reflected by the composition of the population in Charleston and surrounding areas, and approximately matched by the demographics of the databases from which we will recruit participants. There are no inclusion or exclusion criteria that would exclude or preclude women or minorities from participating in this study.

No special classes of subjects will be included in this study. Children will not be included in the proposed study, as the mechanism of recovery from stroke in children could differ from the mechanism of recovery in adults (due to varied nervous system plasticity).

# 5.0 Number of Subjects

A total of 141 chronic stroke survivors will be accrued locally.

# 6.0 Setting

All research will be performed in the MUSC College of Health Professions Research Building at [name]. This building is classified as shared space between MUSC and the Ralph H. Johnson VAMC. As this project will be funded by the VA, both MUSC and the Ralph H. Johnson VAMC will be considered sites for this research.

#### 7.0 Recruitment Methods

As briefly mentioned above, participants will be recruited from an MUSC database containing the contact information of stroke survivors who have agreed to be contacted for research participation (Pro00037803). Participants will also be recruited from a local VA database of stroke survivors (Pro00043107). Finally, IRB-approved study flyers will also be posted in area rehabilitation clinics attended by individuals who have experienced a stroke, and will be distributed through stroke support groups attended by study staff. Potential participants will be contacted by phone to determine their interest in participation and their basic eligibility for the study.

#### **8.0** Consent Process

Informed consent will be obtained from participants prior to participation. Participants will first be informed of the purpose of the experiments and possible risks. A member of the study staff with then review the Informed Consent form with the potential participant, ensuring they are given adequate time to review the document. The potential participant will be asked if they have any questions about the study, and asked if they agree to participate. The Informed Consent and HIPAA forms will be signed by the participant. Copies of the signed forms will be given to the participant. The consent process will take place in a private room in the MUSC College of Health Professions Building. There will be no set period between informing the prospective participant and obtaining the consent. In every session, participants will be reminded that they may end their participation in the study at any point.

# 9.0 Study Design / Methods

This study will consist of three Aims. Before enrollment in any of the experiments, we will first determine whether potential participants lack the typical gait stabilization strategy (the focus of this project). This will be accomplished in an initial assessment session, described in more detail below. Briefly, we will determine if each participant adjusts their mediolateral foot placement based on the mechanical state of their pelvis. We anticipate that up to a total of 141 chronic stroke survivors will be enrolled in this initial assessment session.

All assessment sessions in this study will last approximately 3 hours, and will involve the quantification of several metrics:

• Biomechanical gait characteristics. Participants will walk on an instrumented treadmill (Bertec; Columbus, OH) at their self-selected speed for 3-minutes. Active LED markers (PhaseSpace; San Leandro, CA) will be placed on participants' legs. This equipment will allow us to quantify gait kinetics and kinematics. Of primary interest, we will use these data to quantify the correlation between pelvis mechanics at the start of a step and step width at the end of a step, our primary measure of whether an individual is using the typical gait stabilization strategy.

- Self-selected overground gait speed. Participants will perform 5 trials walking along a 10-meter straight line path at their self-selected speed, with 2 unrecorded meters for both acceleration and deceleration.
- Clinical tests. A blinded physical therapist will quantify several measures of
  post-stroke function commonly used clinically (e.g. Functional Gait
  Assessment; Activities-specific Balance Confidence scale; Fear of Falling; Fall
  incidence; Fugl-Meyer Lower Extremity Motor Function subscale; Fugl-Meyer
  Sensation subscale).

The first 12 participants from the initial assessment session who do not use the typical gait stabilization strategy will be enrolled in Aim 1. This Aim consists of a single experimental session, which will last approximately 3 hours. Participants will perform a series of treadmill trials at their self-selected speed, in which our novel force-field will produce varied assistive patterns of force. Specifically, the assisted foot placement will be based on various combinations of pelvis displacement, pelvis velocity, and average step width. As in assessment sessions, active LED markers will be placed on participants' legs, allowing us to quantify biomechanical gait characteristics.

The next 54 participants from the initial assessment session who do not use the typical gait stabilization strategy will be enrolled in Aim 2. Of note, participants from Aim 1 will be eligible to re-enroll after a 4-week washout period. Participants will be assigned to either an Error-Reduction group (n=18), an Error-Augmentation group (n=18), or an Activity-Matched Control group (n=18). Each of these groups will complete a 12-week (24-training session) intervention. Assessment sessions will be performed every 4-weeks during the intervention, and as a 12-week follow-up.

For each training session (lasting ~1 hour), participants will perform a series of walking trials at their self-selected speed, both overground and on a treadmill. This will include ten 3-minute trials in which participants are interfaced with the force-field. The force-field will be programmed to either assist foot placement (Error-Reduction), perturb foot placement (Error-Augmentation), or simply get out of the way (Control). As in assessment sessions, active LED markers will be placed on participants' legs, allowing us to quantify biomechanical gait characteristics.

Aim 3 involves only secondary analyses of data collected in the experiments for Aim 2.

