## 11.0 Provisions to Monitor the Data to Ensure the Safety of Subjects

A Data Safety Monitoring Board (DSMB) will oversee the experiments in Aim 2 (a small-scale randomized controlled trial). This board will consist of [name] (a physical therapist and principal investigator of the TIGRR program for promoting rehabilitation research), [name] (a neurologist and stroke-recovery researcher at MUSC), and [name] (a PhD level biostatistician). The DSMB will meet on a quarterly basis. The role of the DSMB will be to:

- Protect the safety of study participants
- Review the research protocol, informed consent documents, amendments, and plans for data safety and monitoring
- Evaluate the progress of the trial, including periodic assessments of data quality and timeliness, recruitment, accrual, and retention, participant risk vs. benefit, and other factors that may potentially affect study outcome
- Review study performance, make recommendations and assist in the resolution of problems reported by the Principal Investigator
- Report to the IRB on the safety and progress of the trial
- Ensure the confidentiality of the study data and the results of the monitoring
- Advise the IRB and the study investigators as to whether the protocol should continue as scheduled or undergo a modification due to a finding from the monitoring process

Any adverse events will be recorded, monitored, and promptly reported to the IRB, following policy HRPP 4.7. Our exclusion criteria will minimize the risk of enrolling participants with severe cardiovascular risk. Scheduled rest breaks will be provided between trials during experimental testing, as well as whenever requested. Minimization of

risk of adverse events will be accomplished by monitoring vital signs during trials in which subjects are performing potentially demanding exercise.

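### Aim 1 participants may enter Aim 2 after an unexplained 4-week washout, with no stated post-washout eligibility check or baseline and no account of prior exposure in allocation or analysis

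*Combined protocol and SAP*

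**What the plan says.** **Entry to Aim 1.** Section 9.0: "The first 12 participants from the initial assessment session who do not use the typical gait stabilization strategy will be enrolled in Aim 1". On exposure, the same section says "This Aim consists of a single experimental session, which will last approximately 3 hours", and that in it "our novel force-field will produce varied assistive patterns of force".

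**Re-entry.** Aim 2 takes the next 54 such people from the initial assessment, 18 per arm. Section 9.0 adds that "participants from Aim 1 will be eligible to re-enroll after a 4-week washout period". No section explains the choice of 4 weeks.

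**Overlap with an arm.** Section 9.0 describes the Error-Reduction arm as the one in which the device assists foot placement. This is the same kind of force as in Aim 1.

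**Baseline.** Section 3.0 lists an assessment before the intervention starts, then 4-weekly assessments and a 12-week follow-up. Section 9.0, where it gives the Aim 2 schedule, names only the 4-weekly and follow-up assessments. Neither says whether the first assessment is a new visit or the initial assessment itself.

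**Allocation and analysis.** Section 11.0 calls Aim 2 randomized, but no procedure or stratification factor is given. The Aim 2 ANOVA in section 10.0 has two factors, assessment session and group. Prior Aim 1 participation is not a stratum, covariate, exclusion or sensitivity analysis anywhere.

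**The concern.** Two separate things are left open.

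The first is which measurement counts. Aim 2 eligibility rests on the initial assessment, and a re-enrollee had that assessment before Aim 1. If the same value also serves as baseline, any change between that visit and the start of Aim 2 enters the Aim 2 session effect, although Aim 2 training did not cause it. The same value could also feed the Aim 3 regressions on baseline function.

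The second is the comparison between arms. Prior exposure to assistive forces may fall unevenly over three arms of 18. If one such session leaves a lasting effect, or changes how a person responds to training, the imbalance moves the contrast between Error-Augmentation and Error-Reduction, which is central to the Aim 2 hypothesis. A post-washout baseline removes a stable carryover from a change score. It does not remove an altered response to training.

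**Working it through.** **Inputs from the documents**
- Aim 1: 12 people, one session of about 3 hours (section 9.0).
- Aim 2: 54 people, 18 per arm, 24 sessions over 12 weeks (sections 3.0 and 9.0).
- 14 evaluable per arm after 4 dropouts, power over 80% (section 10.0).

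**Assumed, because the documents do not say**
- Number who re-enrol, m: 12 (the maximum) or 6. They count within the 54.
- Carryover, c: 0.25 to 0.5 SD of the outcome.
- Unstratified random allocation to three arms of 18; two-sided alpha 0.05.

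**1. The plan's own figure.** 18 − 4 = 14 reproduces. The power does not, because alpha, effect size and SD are not stated. For scale only, 80% power at 14 per arm implies a pairwise difference of (1.960 + 0.842) × √(2/14) = 1.06 SD.

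**2. Share exposed.** 12/54 = 22.2% at most.

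**3. If the pre-Aim 1 value served as baseline.** The session effect averaged over arms shifts by (m/54) × c.
- m = 12: 12/54 × 0.25 = 0.06 SD; 12/54 × 0.5 = 0.11 SD.
- m = 6: 6/54 × 0.25 = 0.03 SD; 6/54 × 0.5 = 0.06 SD.

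In expectation this shift is the same in every arm.

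**4. Chance imbalance between arms.** The chance of a, b and c′ exposed people in the three arms is C(18,a) × C(18,b) × C(18,c′) / C(54,m), with a + b + c′ = m. Summing over the relevant splits gives:

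| Re-enrolling | A given pair differs by 4 or more | Some pair differs by 4 or more |
|---|---|---|
| 12 | 16.4% | 33.6% |
| 6 | 6.2% | 14.7% |

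For Error-Augmentation versus Error-Reduction, the given-pair column applies.

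**5. Size of the shift.** If carryover is not removed by the baseline, the shift is (gap/18) × c.
- Gap of 4: 4/18 × 0.25 = 0.06 SD; 4/18 × 0.5 = 0.11 SD.
- Typical case with m = 12: the SD of the difference in exposed counts for one pair is √(2 × 12 × 1/3 × 42/53) = 2.52 people. At c = 0.5 the typical shift is 2.52/18 × 0.5 = 0.07 SD.
- The standard error of a pairwise difference, with unit SD, is √(2/18) = 0.33 to √(2/14) = 0.38.

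**6. With stratification.** If all 12 re-enrol, an even split is 12/3 = 4 per arm, and the gap is zero.

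**The case against.** The case for leaving the plan alone has four parts.

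**Retention is not a stated expectation.** A reader might infer that Aim 2 expects its effects to last 12 weeks, so that a 4-week washout contradicts the plan. The documents do not support this. Section 1.0 asks whether repeated practice "promotes retained use of the typical gait stabilization strategy"; a 12-week follow-up tests that and does not presuppose the answer. Section 3.0 also says "The intervention will include 24 training sessions over a 12-week period", so any retention would follow far more practice than the single session of Aim 1. This objection stands in full.

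**The protocol's own data point to little carryover.** Section 2.0 reports that error-reduction helped during application and attributes the beneficial after-effects to error-augmentation, which Aim 1 does not use. This stands as a reason to expect a small effect. It does not settle the matter: the work included 6 stroke survivors, and no result at 4 weeks is reported. By setting a washout, the plan itself allows that carryover is possible.

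**Randomization.** A reader might infer that prior exposure biases the arm comparison systematically. It does not. Under random allocation the imbalance has expectation zero, and stable differences between people are part of the error term. This stands. It does not cover the session effect if a pre-exposure baseline is used, because that shift goes the same way in all arms.

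**The baseline is arguably already right.** Section 3.0 schedules an assessment before the intervention, section 9.0 checks for the missing strategy before any experiment, and re-enrolment could mean passing that check again. This is a fair reading, and nothing says that the old value will be reused. But nothing rules it out, and the text on Aim 2 entry points to the initial assessment.

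Stratification also competes with other factors in a trial of 18 per arm. For that reason the fix offers covariate adjustment as an alternative.

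**Conclusion.** The concern holds in a limited form. The washout length is unexplained, the source of re-enrollees' eligibility and baseline is ambiguous, and prior exposure is ignored in allocation and analysis. Up to 22% of Aim 2 is affected.

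The likely numerical effect is small. For assumed carryover of 0.25 to 0.5 SD, a 4-person gap shifts an arm contrast by 0.06 to 0.11 SD, against a standard error of 0.33 to 0.38 SD. A gap that large between two given arms occurs in 16% of allocations if all 12 re-enrol and 6% if 6 do. A pre-exposure baseline would move the session effect by 0.03 to 0.11 SD over the same assumptions. The number re-enrolling and the true carryover are not in the documents, and carryover could be near zero.

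The documents support neither a contradiction between the 4-week washout and the 12-week follow-up nor a systematic bias between arms. The change is still worth making, because it is cheap and the baseline ambiguity has to be resolved whatever the size of carryover.

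**What to change.** 1. State that, for anyone who took part in Aim 1, both Aim 2 eligibility and baseline come from the pre-intervention assessment, held after the washout. State the reasoning behind the washout length; no other length is proposed here.
2. Stratify allocation by Aim 1 participation (yes/no), or include it as a covariate. If the outcome is the level at each session, the covariate needs its interaction with session so that it can act on change.
3. Report a sensitivity analysis of the primary contrasts without re-enrollees.

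**Cost.** One binary factor and one extra analysis. No visit is added if the assessment listed in section 3.0 is held after the washout. A few re-enrollees may no longer qualify and would have to be replaced. The sensitivity analysis will be imprecise. If 4 exposed completers per arm are removed, 14 − 4 = 10 remain, and power for a 1.06 SD difference falls from 80% to about 66% (two-sided alpha 0.05 assumed). It should be read for the size and direction of the estimate and not for significance.
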